#### 6.4. Study Compliance

Evidation study staff will track whether participants are completing study-related tasks throughout the study. Participants who do not complete study activities may be contacted by email, text message, or push notifications with reminders to complete activities, within a time window that is appropriate to the specific task, but will remain in the study sample regardless of whether they submit data in a timely manner.

#### 6.5. Compensation

Participants in both arms will be compensated for completing surveys. Participants in the CVD-I will be compensated minimally for the completion of intervention tasks (e.g., completing short quizzes, scheduling a date for their influenza vaccine, reading an article to learn more about the flu, the flu shot, and their cardiovascular conditions), to avoid incentivizing vaccination status unequally between the two arms. The compensation amounts will be detailed in the Data Usage & Permissions Agreements at the beginning of each survey for CVD-I and CVD-C arms, and in the offer to complete the intervention messages for the CVD-I arm. All compensation will be awarded in Achievement Points, of which 100 points is equivalent to \$0.10. Points can be redeemed for monetary compensation or donated to charitable organizations. The following compensation will be awarded: 50 points per intervention message completed, 3 points per optional informational email requested, and 300 points per survey completed. The maximum number of points possible is 1,518 points, which could be redeemed for approximately \$1.52.

### 6.6. Study Flow Diagram

Version 1 13 of 22

Note. Dates are approximate.

#### 7. **Data Types and Outcomes**

- Data from self-reported survey:
  - Demographics
  - Medical history
  - Health behaviors
  - Healthcare utilization
  - Influenza vaccination status, experience, and complications
  - COVID-19 experiences
  - Vaccine attitudes and barriers
  - Influenza risks and healthcare provider role
  - Experience and perceptions of intervention materials (CVD-I only)
- Data from engagement with interventions (CVD-I only)
  - For example, clicks, dismissals, or completions of interventions
- Data from Achievement Profile
  - Activity data generated by wearables (e.g., heart rate, sleep, step data), from 12 months before participation and 12 months after participation (if available)

	Source	Retrospective	Demographics	Baseline	Month 3	Month 6
--	--------	---------------	--------------	----------	---------	---------

Version 1 14 of 22

		12 months before to 12 months after	Survey			
Self-reported data						
Demographics	Survey		X			
Medical history	Survey		X			
Health behavior history & influenza vaccination	Survey		X			
Healthcare utilization	Survey			X	X	X
Influenza vaccination status	Survey			X	X	X
Influenza experience & complications	Survey			X	X	X
COVID-19 experiences & perceptions	Survey			X	X	X
Vaccine drivers & barriers	Survey			X	X	X
Influenza risks & healthcare provider role	Survey			X	X	X
Experience and perceptions of intervention materials	Survey					X (CVD-I only)
Engagement with interventions	Achievement website/app and Survey Monkey		[] (CVD-I only)			
Activity tracker data						
Steps	[e.g. Fitbit, Garmin]	X	[]			
Sleep	[e.g. Fitbit, Beddit]	X	[]			
Heart rate	[e.g. Fitbit, Apple]	X	[]			

# 8. Statistical Considerations

Version 1 15 of 22

#### 8.1. Sample Size Justification

We determined sample size for a two-arm interventional statistical superiority study design with vaccination rates as the primary outcome of interest (Zhong 2009). Studies on the impact of messaging and reminders to improve influenza vaccination rates show a range of effect sizes from 2.5 - 3.5% (Nehme et al., 2019, Hurley et al., 2018). As noted earlier, CDC reported vaccination rates are 47.9% for adults between the ages of 18 - 65.

Given these a-priori assumptions, we assumed different baseline vaccination rates of 35%, 50% and 60%, and then computed the sample size needed to detect an increase in vaccination rate of 2%, 3% and 4% respectively. Sample size for the difference in proportion is determined by (Zhong, 2009):

$$N = \frac{1}{2} \left( \frac{z_{\alpha/2} + z_{\beta}}{arcsin\sqrt{p} - arcsin\sqrt{p_0}} \right)^2$$

#### Where:

 $Z_{\alpha/2}$  and  $Z_{\beta}$  refer to the z critical values for a type I and II error of 0.05 and 0.2 respectively,  $p_0$  and p are the baseline proportion and the new hypothesized proportion respectively, and N is the total sample size, assuming a 1:1 ratio of intervention to control

Baseline vaccination rate	Hypothesized vaccination rate	Hypothesized effect size	Hypothesized Cohen's h	Sample size
35.0%	37.0%	2.0%	4.2%	18080
50.0%	52.0%	2.0%	4.0%	19610
60.0%	62.0%	2.0%	4.1%	18668
35.0%	38.0%	3.0%	6.2%	8080
50.0%	53.0%	3.0%	6.0%	8710
60.0%	63.0%	3.0%	6.2%	8256
35.0%	39.0%	4.0%	8.3%	4570
50.0%	54.0%	4.0%	8.0%	4894
60.0%	64.0%	4.0%	8.2%	4618

In the above table, for each baseline rate and hypothesized rate increase (and associated Cohen's h), we show the estimated total sample size needed for each assumption of baseline vaccination

Version 1 16 of 22

rate and effect size. We note that within each hypothesized effect size, changing assumptions about baseline vaccination rates do not substantially alter the sample size.

Based on this, we believe that a 3% effect size is a reasonable assumption and that a sample size of approximately 8000 participants will be needed to detect this difference with a type I error rate of 0.05 and a presumed power of 0.80. A participation dropoff of 67% has been observed for digital interventions for increasing influenza vaccination (i.e., Samson et al., 2020). Assuming between 67% to 75% dropoff for this study, we estimate that between 24,000 - 35,000 participants will need to be recruited and randomized for this study. Based on these calculations, we plan to recruit approximately 35,000 participants.

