### 3. Study Design

### 3.1. Overall Design

- A 6-month prospective, digital randomized controlled trial targeting approximately 35,000 individuals to evaluate the effectiveness of an influenza vaccination intervention during influenza season for people with cardiovascular conditions
- Two study arms: cardiovascular disorders digital intervention arm (CVD-I) & cardiovascular disorders without digital intervention arm (control: CVD-C)

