Based on this, we believe that a 3% effect size is a reasonable assumption and that a sample size of approximately 8,000 participants will be needed to detect this difference with a type I error rate of 0.05 and a presumed power of 0.80. A participation drop-off of 67% has been observed for digital interventions for increasing influenza vaccination in people with diabetes (i.e., Samson et al., 2020). A recent internal survey of individuals with cardiovascular disease demonstrated a survey completion rate of approximately 7%, indicating that this population may have lower than expected engagement. Based on these calculations, we plan to recruit approximately 49,000 participants, anticipating that on average, engagement may be approximately 16%. A targeted enrollment list of approximately 49,000 individuals with 16% survey completion would reach the estimated analysis population of 8,000 participants needed.

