6 MODIFICATIONS TO THE STATISTICAL SECTION OF THE PROTOCOL

The exploratory objective, "To describe self-reported complications from influenza experienced by individuals with different cardiovascular conditions during the 6-month study period, as well as differences in complications by vaccination status" has been removed from analysis because the survey questions did not ask about specific complications of influenza.

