8 STATISTICAL METHODS

8.1 General Statistical Approaches

For the study variables, we will perform distributional analysis. When describing the study population, we will use min, max, mean, and standard deviations for continuous variables (i.e. age, BMI) and frequency counts for categorical variables (i.e. gender, ethnicity). For both continuous and categorical variables, we will report on the number of participants evaluated for that variable, as well as the number of people with non-missing values. For the study variables, we will also look at individual-level rates of missing data. Missing data or unknown responses will be described separately and not be counted in the summary descriptions of the variables. We will report on the percent of missing data for each of the included data sources (surveys, activity data) and evaluate whether any missingness is associated with baseline participant-level characteristics in the case of missing survey data or with the outcome in the case of activity tracker data.

Statistical testing comparing variables will be performed at the 5% significance level using two-sided tests or two-sided 95% confidence intervals (CI), unless otherwise specified. Comparison of means will use Student's t-test for normal distributions, or a Mann-Whitney U test for non-normal distributions. Comparisons of frequencies will use chi-square tests. Regression modeling approaches are described below. We will report on the size of the beta-parameter estimate and the associated significance level (p-value) for each predictor variable.

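### Protocol and SAP plan different numbers to randomise (about 35,000 and about 49,000) for the same 0.80 power; SAP 6 does not list the change, and neither number gives 80% power at the SAP's 16% engagement

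*Protocol*

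**What the plan says.** The protocol gives about 35,000 in the Protocol Summary, in 3.1 ("A 6-month prospective, digital randomized controlled trial targeting approximately 35,000 individuals") and in 8.1. Section 8.1 shows where it comes from: "Assuming between 67% to 75% dropoff for this study, we estimate that between 24,000 - 35,000 participants will need to be recruited and randomized". It then settles on the upper end: "Based on these calculations, we plan to recruit approximately 35,000 participants". The effect is 3 points ("we believe that a 3% effect size is a reasonable assumption") and the error rates are a "type I error rate of 0.05 and a presumed power of 0.80".

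SAP 4 repeats the same formula, table, effect, target of about 8,000 analysed and 0.80 power. It cites an internal survey of people with cardiovascular disease with about 7% completion, and then says "we plan to recruit approximately 49,000 participants, anticipating that on average, engagement may be approximately 16" per cent.

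SAP 6 is the section for modifications to the protocol's statistical section. Its one entry is an exploratory objective on influenza complications, which "has been removed from analysis because the survey questions did not ask about specific complications of influenza". It lists no change to the sample size. The figure 35,000 appears nowhere in the SAP.

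SAP 8.2 defines the primary analysis population (P1) as responders to the 3-month or 6-month survey.

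**The concern.** Two documents for one trial give different numbers to randomise, 14,000 apart (49,000 / 35,000 = 1.40), on different retention assumptions: 25–33% in the protocol, 16% in the SAP. Someone who relies on SAP 6 to learn what has changed would conclude that Protocol 8.1 still stands. When the SAP 8.3 flow chart reports the number assigned to each arm, at least one document will not match it.

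Because the primary analysis uses survey responders, the analysed number is the list size multiplied by the response rate, and that product sets the power. Both documents state 0.80. It needs to be checked whether either list size delivers that at the response rate the sponsor now expects.

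**Working it through.** **Inputs.** Type I error 0.05, power 0.80, 1:1 allocation, a 3-point increase, and baselines of 35%, 50% and 60% (Protocol 8.1, SAP 4). The tests are two-sided: the formula uses the α/2 critical value, and SAP 8.1 has comparisons "performed at the 5% significance level using two-sided tests". I add a 47.9% baseline because both documents cite it as the reported rate.

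**1. Reproduce the table.** Let d = arcsin√p − arcsin√p₀. The printed formula is ½ × ((1.96 + 0.8416)/d)². Although it is labelled as a total, it gives the number per arm. Doubled, it reproduces the printed totals for +3 points:

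| Baseline | d | Formula (per arm) | Doubled | Printed |
|---|---|---|---|---|
| 35% | 0.03116 | 4,041.0 | 8,082 | 8,080 |
| 50% | 0.03002 | 4,355.3 | 8,711 | 8,710 |
| 60% | 0.03083 | 4,128.3 | 8,257 | 8,256 |

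The table values are therefore correct totals, and the label does not affect what follows.

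**2. Reproduce the numbers to randomise.**

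- Protocol lower end: 8,000 / 0.33 = 24,242 (stated 24,000).
- Protocol upper end: 8,710 / 0.25 = 34,840 (stated 35,000). With 8,000 it would be 32,000, so the upper end matches the largest 3-point row rather than the rounded 8,000.
- SAP: 8,000 / 0.16 = 50,000 (stated about 49,000). In the other direction, 49,000 × 0.16 = 7,840, which is below all three table values of 8,080, 8,710 and 8,256.

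**3. Power for +3 points.** With N the total analysed, power = Φ(d × √N − 1.96). For example, at a 50% baseline and N = 7,840: 0.03002 × 88.54 = 2.658; 2.658 − 1.96 = 0.698; Φ(0.698) = 0.757.

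| List × response | N analysed | 35% | 47.9% | 50% | 60% |
|---|---|---|---|---|---|
| 35,000 × 25% (protocol's own worst case) | 8,750 | 83.0% | 80.1% | 80.2% | 82.2% |
| 49,000 × 16% (SAP's own pairing) | 7,840 | 78.8% | 75.7% | 75.7% | 77.9% |
| 35,000 × 16% (mixed) | 5,600 | 64.5% | 61.2% | 61.3% | 63.6% |

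**4. Engagement at which 49,000 would reach 80%.** From the smallest and largest 3-point rows: 8,080 / 49,000 = 16.5% and 8,710 / 49,000 = 17.8%. The SAP's 16% is just under this range.

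**The case against.** Each document is coherent, or nearly so, on its own terms. The protocol pairs 35,000 with 25–33% retention and reaches 80% even at the lower end. The SAP lowered expected engagement and raised the list in the same paragraph, printing the new number and the reason for it. SAP 2 also restates the design without the protocol's 35,000. The SAP reads as the later document, and updating a planning assumption there is ordinary practice. All of this stands. It makes the change openly stated but unlisted, and it means that the protocol's arithmetic is not at fault.

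Three stronger readings are tempting, and the documents do not support them.

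- A reader might infer that the trial is planned at 61–65% power. That figure pairs the protocol's list with the SAP's response rate, a combination that neither document plans. It applies only if about 35,000 were randomised and 16% responded.
- A reader might infer that a null result from 5,600 responders would say nothing about a 3-point effect. With 2,800 per arm, the half-width of the 95% interval at a 50% rate is 1.96 × √(2 × 0.25 / 2,800) = 2.6 points, so an estimate near zero would exclude +3. Only non-significant estimates above about 0.4 points (3 − 2.6) would leave +3 inside the interval.
- A reader might infer that 35,000 is certainly still in force, or that the list was fixed in a single randomisation. The documents say only that randomisation comes before activities are offered. The protocol supplied is Version 1, and whether it was later amended cannot be seen from these documents.

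The objection does not remove the gap in SAP 6, the conflict between the two current texts, or the shortfall at the SAP's own inputs.

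**Conclusion.** The concern holds as an inconsistency between documents, together with a power statement that the SAP's own inputs do not quite meet. The planned numbers to randomise differ by 14,000 (40%), and the change is missing from the section meant to record it. At the SAP's 49,000 and 16%, power for +3 points is about 76–79%, a shortfall of about 1 to 4 points from the stated 0.80. The larger shortfall, to about 61–65%, is conditional on about 35,000 having been randomised.

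These figures assume a two-sided 5% test, equal analysed numbers per arm, a true 3-point increase, baselines of 35–60%, and 16% of the list entering P1. They are sensitive to the last of these. If engagement matched the roughly 7% completion in the SAP's internal survey, 49,000 would give 3,430 responders and about 42–45% power. That is the edge of the range shown in the documents, not the SAP's expectation.

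**What to change.** 1. Add an entry to SAP 6 giving the revised number to randomise, the revised engagement assumption (about 16%, in place of 67–75% drop-off) and the reason already given in SAP 4.
2. Make the Protocol Summary, Protocol 3.1, Protocol 8.1 and SAP 4 state the same number to randomise. If randomisation has already taken place, use the number actually randomised, and keep the record of the change in SAP 6 so that the protocol's initial assumption is not rewritten without trace.
3. Restate the power in SAP 4 for that number: about 76–79% for a 3-point increase at 49,000 × 16% = 7,840, or about 61–65% at 35,000 × 16% = 5,600 if about 35,000 were randomised. Copying 49,000 into the protocol while leaving 0.80 in place would not resolve the point.

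The cost is a text change to each document; the protocol's Statement of Compliance already requires IRB approval for any protocol amendment. No extra enrolment is needed. The only downside is that a less favourable power is stated openly.

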#### 8.2. Description of Analytical Plan

### 8.2.1. Baseline Descriptive Statistics

Descriptive statistics (e.g., mean, standard deviation, frequency and percentage) of study participants will be reported for demographic variables (e.g., age, gender, education, income) and patient reported outcomes (e.g., vaccination rates). To confirm that block randomization is successful, we will compare the intervention to control groups in terms of baseline demographics, vaccine drivers/barriers, and vaccine knowledge for each of the block groups described earlier.

### 8.2.2. Analysis of Primary Endpoint

An intention to treat analysis will be conducted of the primary outcomes for the study. Assuming that a descriptive comparison of the intervention to control group does not demonstrate statistically significant differences in terms of demographics, vaccine drivers/barriers, or vaccine knowledge, we will report on the relative rate of influenza vaccination for the intervention group compared to the control group. We will also conduct logistic regression modeling of influenza vaccination as follows:

$$logit(Y) = \beta_0 + \beta_1 M + \sum_{j} \beta_j \alpha_j + \varepsilon$$

Where:

logit(Y) = ln(Y/1-Y) for the binary variable designation of influenza vaccination status M = the binary designation for Intervention (messaging) vs Control (no messaging)  $\alpha_j =$  the baseline covariates measured in the study (e.g. demographics, vaccine drivers/barriers or knowledge)

 $\varepsilon$  = the error term of the regression.

For the logistic regression model the p-values associated with each of the  $\beta$  parameter estimates will be reported.

Version 1 17 of 22

#### 8.2.3. Analysis of Secondary Endpoint

To examine differences in vaccination rates between individuals in the CVD-I group and its relationship to engagement with intervention messages, we will model:

$$logit(Y) = \beta_0 + \beta_1 M + \sum_i \beta_i \alpha_i + \varepsilon$$

Where:

logit(Y) = ln(Y/1-Y) for the binary variable designation of influenza status

M = the number of engaged messages (ordinal variable 0, 1, 2, 3, 4, 5, 6)

 $\alpha_j$  = the baseline covariates measured in the study (e.g. demographics, vaccine drivers/barriers, or knowledge)

To examine predictors of vaccination status, including cardiovascular condition type, vaccine drivers/barriers, and vaccine knowledge, across CVD-I and CVD-C we will construct the model:

$$logit(Y) = \beta_0 + \beta_1 P + \sum_i \beta_i \alpha_i + \varepsilon$$

Where:

logit(Y) = ln(Y/1-Y) for the binary variable designation of influenza status

 $C_i$  = the binary designation Cardiovascular Condition as described earlier

P = the predictor of interest (e.g. cardiovascular condition, vaccine drivers/barriers, vaccine knowledge index)

 $\alpha_j$  = the baseline covariates measured in the study (e.g. demographics, vaccine drivers/barriers, or knowledge)

 $\varepsilon$  = the error term of the regression.

To examine predictors of vaccination status, including cardiovascular condition type, vaccine drivers/barriers, and vaccine knowledge, within CVD-I or CVD-C we will construct the model:

$$logit(Y) = \beta_0 + \beta_1 M + \beta_2 P + \sum_i \beta_i \alpha_i + \varepsilon$$

Where:

logit(Y) = ln(Y/1-Y) for the binary variable designation of influenza status

M = the messaging group being examined (either Intervention or Control)

P = the predictor of interest (e.g. cardiovascular condition, vaccine drivers/barriers, vaccine knowledge index)

 $\alpha_j$  = the baseline covariates measured in the study (e.g. demographics, vaccine drivers/barriers, or knowledge)

 $\varepsilon$  = the error term of the regression.

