#### 2.2. Secondary Objectives

- To examine differences in vaccination rates between individuals in CVD-I who engaged with different numbers of intervention messages, and changes in self-reported vaccination rates following intervention messages
- To describe levels of engagement with the intervention messages and perceptions of the intervention messages within the CVD-I group
- To examine predictors of vaccination status, including cardiovascular condition type, vaccine drivers/barriers, and vaccine knowledge, across diagnoses and within CVD-I and CVD-C groups

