8.2 Analysis Population (s)

The analysis populations will consist of:

- P1: This population will consist of all individuals who respond to the 3-month or 6-month survey. It will
 be used for the primary objective analysis and for the first part of the secondary objective (examine
 predictors of vaccination status across the CVD-I and CVD-C arms). This population will also be used
 for the second exploratory objective, which is to describe self-reported complications from influenza
 during the study period.
- P2: This population will consist of all individuals who are in the CVD-I arm and have responded to the 3-month or 6-month survey. It will be used for the second part of the secondary objective, which is to describe the engagement with different intervention messages and its relationship to influenza vaccination status.
- P3a: This population will consist of individuals who responded to the baseline, 3-month or 6-month survey. It will be used to examine the first part of the exploratory objectives - specifically the selfreported impact of COVID-19 on influenza vaccination and behavior.
- P3b: This population will consist of all individuals who complete either the 3-month or the 6-month survey, who have wearable activity data and who consent in the final (6-month) survey to have the activity data analyzed for this study. This population will be used for the 3rd exploratory objective, specifically to explore the differences in wearable data (i.e., sleep, steps, heart rate) between individuals who experience influenza and those who do not, as well as differences in wearable data between cardiovascular conditions.

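### The engagement model gives one odds ratio per message; it tests for trend but cannot show which message counts differ, and a none-versus-any difference can look like a gain from each extra message

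*Protocol*

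**What the plan says.** Protocol 2.2 sets the secondary question: "To examine differences in vaccination rates between individuals in CVD-I who engaged with different numbers of intervention messages". Protocol 8.2.3 answers it with a logistic model, introduced by "To examine differences in vaccination rates between individuals in the CVD-I group and its relationship to engagement with intervention messages, we will model". The model is logit(Y) = b0 + b1·M + covariates, where "M = the number of engaged messages (ordinal variable 0, 1, 2, 3, 4, 5, 6". SAP 8.6.2 writes the same single b1·M term with the same definition of M.

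The population is set in SAP 8.2: "P2: This population will consist of all individuals who are in the CVD-I arm and have responded to the 3-month or 6-month survey". On output, SAP 8.1 says "We will report on the size of the beta-parameter estimate and the associated significance level (p-value) for each predictor variable".

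Neither document says how M is coded. Neither plans vaccination rates by message count, indicator terms for M, or a check of linearity.

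**The concern.** One coefficient on M imposes the same odds ratio on the step from 0 to 1 as on the step from 5 to 6. Yet the first step separates people who never engaged from everyone else. Engagement is optional in CVD-I, and SAP section 4 expects it to be low, so a jump at the first message followed by a plateau is plausible.

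Under that pattern the planned output is one positive odds ratio per message. A reader would naturally take it to mean that each further message goes with more vaccination, and no planned table would correct this. The number of messages worth sending is a practical question that users of the result may well put to it.

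**Working it through.** **Inputs from the documents**
- M runs from 0 to 6. The points total in Protocol 6.5 agrees with six messages: 4 × 300 + 6 × 50 + 6 × 3 = 1,518.
- Analysed total: SAP section 4 says its enrolment list "would reach the estimated analysis population of 8,000 participants needed". At 1:1 allocation this gives 8,000 / 2 = 4,000 in CVD-I.
- Low case: SAP section 4 also reports "a survey completion rate of approximately 7"% in an internal survey. 0.07 × 49,000 = 3,430, or 1,715 in CVD-I.
- Tests are two-sided at 5% (SAP 8.1).

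The documents give no power or sample size for this model, so there is no stated figure to reproduce.

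**Assumptions not in the documents:** the spread of M and the true rate at each count. Covariates are left out.

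**Worked example.** N = 4,000, half at M = 0 and one twelfth at each of 1 to 6. True rates are 50% at 0 and 56% at every other count. A large-sample fit of the one-term model gives
- fitted logit = 0.0386 + 0.0468·M, SE of slope 0.0150
- OR = exp(0.0468) = 1.048; 95% CI exp(0.0468 ± 1.96 × 0.0150) = 1.018 to 1.079
- fitted rates 51.0% at 0, 52.1% at 1 and 57.9% at 6
- rise from one message to six: 57.9 − 52.1 = 5.8 points (truth 0)
- first message: 52.1 − 51.0 = 1.1 points (truth 6)
- chance of a significant positive slope: z = 3.13, Φ(3.13 − 1.96) = 88%

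**Same spread, 3-point step (50% then 53%).** The documents' planning effect is 3 points, though for the comparison between arms. The slope is 0.0233 with SE 0.0149, so OR 1.024 (0.994 to 1.054). z = 1.56 and Φ(1.56 − 1.96) = 35%. At N = 1,715 the SE is 0.0228, z = 1.02, and the chance is 17%.

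**Other spreads, N = 4,000, step at the first message only**

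| Spread of M | 3-point step: OR; significant and positive | 10-point step: OR; fitted rate at 1 and at 6; significant and positive |
|---|---|---|
| Uniform over 0 to 6 | 1.013; 13% | 1.045; 56.4%, 61.8%; 79% |
| 50% at 0, rest even | 1.024; 35% | 1.082; 53.6%, 63.1%; >99% |
| 40% at 0, 30% at 6 | 1.019; 35% | 1.067; 53.3%, 61.2%; >99% |
| 80% at 0 | 1.027; 27% | 1.094; 52.7%, 63.6%; >99% |

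In the last column the true rate is a flat 60% from 1 to 6. In simulation (first two spreads, 10-point step), a slope fitted only among people with M ≥ 1 was significant and positive in 2.3% to 2.5% of trials, the nominal rate. The apparent trend therefore comes from the step at zero.

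**No association at any count.** OR 1.000, significant and positive in about 2.5%.

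**Truth linear on the logit scale, 50% to 60% over 0 to 6.** Power is 92% to >99% for the one-term test and 71% to >99% for a 6-df test of M as categories.

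**Precision of a category contrast.** In the worked example the difference between one count and zero has half-width 1.96 × √(0.25/2,000 + 0.56 × 0.44/333) = 5.8 points. At N = 1,715 it is 1.96 × √(0.25/857.5 + 0.56 × 0.44/143) = 8.8 points.

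**The case against.** A reader might infer that the model cannot show any difference between message counts. That goes too far. A 1-df term is a valid test for trend across ordered counts and, as shown above, usually the more powerful one if the relation is roughly linear. What it cannot give is shape or contrasts between particular counts.

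A reader might also infer that the model will report a per-message gain whenever extra messages add nothing. It does so only if there is a threshold, such as none versus any. The example's 6-point step and its spread of M are assumptions, and with a 3-point step significance is not the expected result.

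Nor is straight-line coding certain. Protocol 8.2.3 uses the same one-coefficient notation for a variable that cannot be a single slope: "P = the predictor of interest (e.g. cardiovascular condition, vaccine drivers/barriers, vaccine knowledge index". Cardiovascular condition has seven categories in SAP 7.1, so the equations may be schematic. A count also has equal steps in message units, and ordinal may be a loose label. This objection stands as far as it goes, but its result is that the coding of M is unstated, and the same edit resolves that.

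The stakes are limited too. This is a secondary, non-randomised association within one arm, and the primary comparison is unaffected. SAP 3.2 does not repeat the Protocol's wording about different numbers of messages, and SAP 8.2 speaks only of engagement and its relationship to vaccination, which a trend term can address. SAP 8.1 does provide in general for frequency counts and chi-square tests, but it does not apply them to M.

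**Conclusion.** The point holds as a cheap improvement to a secondary analysis. On its natural reading, the plan returns one slope for a question about specific message counts and includes nothing that would reveal a step or a plateau. If the main difference is between none and any, the slope can be misread as a benefit of each extra message, with a false rise of 5.8 points in the worked example.

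How often that happens depends on quantities the documents do not give: about 88% of trials for a 6-point step and 35% for a 3-point step at N = 4,000 with half at zero. The documents do not support saying that the model must produce a false gain, that the trend test is invalid, or that linear coding has definitely been chosen.

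**What to change.** In SAP 8.6.2, and in Protocol 8.2.3 to match:

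1. State how M is coded. Keep the linear term and label it a trend test.
2. Add a table of adjusted vaccination rates and differences from M = 0, with 95% CIs, from a model with M as categories. Fix any merging of counts in advance, for example 0, 1–2, 3–4, 5–6.
3. Add a test of departure from linearity.
4. State that the slope will not be interpreted as a gain per message without the table.

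The cost is SAP wording and one table from data already planned. Intervals for single counts are wide, as the half-widths above show: a 6-point difference would barely clear its interval at N = 4,000 and would not at 1,715. Merging pairs helps: 1.96 × √(0.25/2,000 + 0.56 × 0.44/667) = 4.4 points at N = 4,000. The linearity test has limited power, about 34% in the worked example and 42% to 80% for a 10-point step across the four spreads. A non-significant result should not be read as support for a straight line, and the table carries most of the information. The trend test keeps its power because it is retained.
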